2.4 Sample Size Calculations (Randomized cohort)

The sample sizes of pivotal IDE trial randomized cohort are estimated based on the primary effectiveness and safety endpoints and tests. The study is powered on combined high and extreme risk cohort. The sample size is calculated to achieve at least 80% power for both primary effectiveness and safety endpoints [REDACTED]

[REDACTED]

[REDACTED]

[REDACTED]

[REDACTED]

[REDACTED]

[REDACTED]

[REDACTED]

Statistical Analysis Plan

[REDACTED]

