1.5 Randomization (Randomized cohort)

Subjects will be randomized per 1:1 ratio to test (Portico) vs. commercially available valve (CAV). group according to a computer-generated randomization scheme. [REDACTED]

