2.3 Endpoint Analysis

2.3.1 Primary Endpoints (Randomized Cohort)

Primary Effectiveness Endpoint

The primary effectiveness endpoint is the composite endpoint of all-cause mortality or disabling stroke at one year. This endpoint will be evaluated by a non-inferiority test comparing the Portico test group to the control (CAV) group, and the primary analysis will be conducted on the ITT population. The primary analysis will be performed based on combined high and extreme risk cohort with pooled access data.

The primary analysis will be conducted on a dataset locked after all enrolled subjects have had their one-year study visit (except those withdrawn or lost-to-follow-up before one year).

Statistical Analysis Plan

[REDACTED]

[REDACTED]

[REDACTED]

[REDACTED]

[REDACTED]

[REDACTED]

Primary Safety Endpoint

The primary safety endpoint is the non-hierarchical composite endpoint of all-cause mortality, disabling stroke, life-threatening bleeding requiring blood transfusion, acute kidney injury requiring dialysis, or major vascular complications at 30 days. This endpoint will be evaluated by a non-inferiority test comparing Portico test group to the control group, and the primary analysis will be conducted on the ITT population. The primary analysis will be performed based on combined high and extreme risk cohort with pooled access data.

[REDACTED]

Statistical Analysis Plan

[REDACTED]

[REDACTED]

[REDACTED]

[REDACTED]

[REDACTED]

[REDACTED]

[REDACTED]

[REDACTED]

[REDACTED]

[REDACTED]

[REDACTED]

[REDACTED]

[REDACTED]

[REDACTED]

[REDACTED]

[REDACTED]

[REDACTED]

[REDACTED]

[REDACTED]

[REDACTED]

[REDACTED]

[REDACTED]

[REDACTED]

[REDACTED]

Statistical Analysis Plan

[REDACTED]

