2.4.3 Total Sample Size

The total sample size required for evaluating the primary effectiveness and safety endpoints is 750 and 750 subjects respectively. Thus, the total sample size is 750 for the pivotal IDE trial randomized cohort.

[REDACTED]

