2.6 Trial Success

Success will be declared when all the primary endpoints are met.

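### Does requiring both primary endpoints leave the trial with well under 80% power at 750 subjects?

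*SAP*

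**What the plan says.** SAP 2.4 sizes the randomized cohort on the two primary endpoints and says: "The sample size is calculated to achieve at least 80% power for both primary effectiveness and safety endpoints". The sentence then runs into redacted text. SAP 2.4.3 adds: "The total sample size required for evaluating the primary effectiveness and safety endpoints is 750 and 750 subjects respectively", and takes 750 as the total; Protocol 11.4.3 gives the same figures.

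SAP 2.3.1 assigns each endpoint its own non-inferiority test in the ITT population. For one-year death or disabling stroke: "This endpoint will be evaluated by a non-inferiority test comparing the Portico test group to the control (CAV) group". For the 30-day safety composite: "This endpoint will be evaluated by a non-inferiority test comparing Portico test group to the control group". Allocation is 1:1 (SAP 1.5), so 375 per arm.

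The success rule in SAP 2.6 is: "Success will be declared when all the primary endpoints are met".

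**The concern.** Success is a joint event, and the power statement reads most naturally as one figure per endpoint: SAP 2.4.3 gives each endpoint its own sample size, whereas a joint calculation would give one sample size for the pair. The probability of passing both tests cannot exceed the smaller of the two individual powers, and it equals that value only if the tests are perfectly correlated or the other test is certain to pass.

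Perfect correlation is not credible here. The endpoints have different horizons, 30 days and one year. They share only deaths and disabling strokes in the first 30 days, and the safety composite adds bleeding, dialysis and vascular complications.

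A reader who sets SAP 2.4 beside SAP 2.6 could therefore take 80% as the chance of a successful trial. If both endpoints sat exactly at 80%, a device performing as assumed would fail the success rule 30% to 36% of the time, not 20%.

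**Working it through.** **Inputs from the documents.** At least 80% power for the primary endpoints (SAP 2.4); 750 for each endpoint and in total (SAP 2.4.3); 1:1 allocation (SAP 1.5); both endpoints needed for success (SAP 2.6). Alpha, event rates, margins, attrition and the actual power of each endpoint are redacted.

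**Can 750 be reproduced?** No. For a non-inferiority comparison of two proportions with equal true rates p and n per arm, the margin that gives power 1 − β is

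margin = √(2p(1 − p)/n) × (z(1 − α) + z(1 − β)).

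Take p = 20% and one-sided α = 0.025 as assumptions, with n = 375. The standard error is √(0.32/375) = 0.0292.

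- 80% power: 0.0292 × (1.960 + 0.842) = 0.082, a margin of 8.2 points.
- 90% power: 0.0292 × (1.960 + 1.282) = 0.095, a margin of 9.5 points.

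The same 750 subjects therefore give 80% or 90% power depending on about 1.3 points of a margin that cannot be seen. The figure of 750 does not show that either endpoint sits at 80%.

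**Joint power.** Let p₁ and p₂ be the individual powers and ρ the correlation of the two test statistics. Joint power is P(Z₁ ≤ z(p₁), Z₂ ≤ z(p₂)) for a standard bivariate normal pair. At ρ = 0 it is the product, for example 0.80 × 0.80 = 0.64 and 0.90 × 0.90 = 0.81.

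| Power per endpoint | ρ = 0 | ρ = 0.3 | ρ = 0.5 | ρ = 0.6 |
|---|---|---|---|---|
| 80% / 80% | 64.0% | 66.6% | 68.7% | 69.9% |
| 80% / 90% | 72.0% | 73.7% | 75.1% | 76.0% |
| 85% / 85% | 72.2% | 74.2% | 75.8% | 76.7% |
| 90% / 90% | 81.0% | 82.2% | 83.2% | 83.9% |

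For 80% joint power with equal individual powers, each endpoint needs √0.80 = 89.4% at ρ = 0, 88.7% at ρ = 0.3 or 87.9% at ρ = 0.5.

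**Plausible correlation.** The documents give none. Let s be the rate of death or disabling stroke within 30 days, and p_S and p_E the rates of the safety and effectiveness endpoints. If the parts not shared are independent among subjects free of those events, the covariance is s(1 − p_S)(1 − p_E)/(1 − s), so

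ρ = [s/(1 − s)] × √[(1 − p_S)(1 − p_E)/(p_S p_E)].

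The rates below are assumptions: s 3–7%, p_S 15–30%, p_E 15–25%.

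- Low end (s = 3%, p_S = 30%, p_E = 25%): 0.0309 × √7 = 0.08.
- High end (s = 7%, p_S = p_E = 15%): 0.0753 × (0.85/0.15) = 0.43.

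Appendix W, section 2.1 of the protocol notes that vascular and bleeding complications go with higher mortality, which would raise these values somewhat. Across 0.08 to 0.43, joint power is 65% to 68% at 80% each and 81% to 83% at 90% each. The unknown individual powers matter far more than the unknown correlation.

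**The case for a change.** The strongest case for acting is that one result needs no redacted input: if either endpoint is at the 80% minimum, joint power is below 80% unless the other is almost certain to pass or the tests are almost perfectly correlated. Even 80% with 95% gives only 76.0% to 78.4% for ρ of 0 to 0.6. The separate sample sizes in SAP 2.4.3 favour the per-endpoint reading, and the remedy would be one sentence.

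The conditional arithmetic and the per-endpoint reading both stand. The step to a figure for this trial does not. SAP 2.4 gives a lower limit, and nothing visible puts either endpoint at it. An identical 750 for both endpoints is at least as consistent with power evaluated at a fixed total, where one or both exceed 80%, as with two separate 80% calculations that happen to agree. The places where actual power, and possibly joint power, would be stated are redacted, so the plan cannot be said to lack them. Nor does the visible text anywhere call 80% the probability of trial success.

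**Conclusion.** The concern does not call for a change. Read per endpoint, the 80% statement is not contradicted by the success rule; read jointly, it cannot be refuted from what is visible. The 64–70% range is correct only if both endpoints have exactly 80% power and the correlation lies between 0 and 0.6. With 80–90% per endpoint and the same correlations, the range is 64% to about 84%, which includes designs with no shortfall.

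This is a question of power only. A rule that needs both tests to succeed does not inflate the type I error, so a false claim of success is no more likely. If joint power is below 80%, the sponsor carries a higher risk of missing success, which is a fair trade-off for not enlarging the trial. For scale, moving from exactly 80% each to 80% jointly at ρ = 0 and one-sided α = 0.025 would take 750 × [(1.960 + 1.250)/(1.960 + 0.842)]² ≈ 985 subjects.

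A sentence giving the joint power and the assumed correlation would help readers, if the redacted text does not already contain one. It would leave the sample size, both tests, the success rule and the conclusions as they are.

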2.4.3 Total Sample Size

The total sample size required for evaluating the primary effectiveness and safety endpoints is 750 and 750 subjects respectively. Thus, the total sample size is 750 for the pivotal IDE trial randomized cohort.

[REDACTED]

2.5 Interim Analysis

No formal interim analyses are planned for this study. [REDACTED]

2.6 Trial Success

Success will be declared when all the primary endpoints are met.

2.7 Subgroups for Analysis (Randomized cohort)

For the primary safety and effectiveness endpoints and secondary endpoints (aortic regurgitation, KCCQ score at one year, 6-minute walk at one year) in the randomized cohort tests will be performed [REDACTED]

[REDACTED]

[REDACTED]

[REDACTED]

[REDACTED]

[REDACTED]

[REDACTED]

[REDACTED]

[REDACTED]

Statistical Analysis Plan

[REDACTED]

2.11 Multiplicity Issues

Multiplicity adjustment will apply to hypothesis testing for the superiority tests of primary endpoints and four non-inferiority tests of secondary endpoints (severe AR, KCCQ, moderate or severe AR, and 6-minute walk) in pivotal IDE trial.

[REDACTED]

[REDACTED]

[REDACTED]

2.12 Adjustments for Covariates

[REDACTED]

3.0 DESCRIPTIVE ENDPOINTS AND ADDITIONAL DATA

3.1 Baseline and Demographic Characteristics

The following baseline and demographic variables will be summarized for the subjects enrolled: gender, age, ethnicity, race, cardiac disease history, arrhythmia history, history of smoking, implant procedural characteristics, etc.

[REDACTED]

Statistical Analysis Plan

3.2 Adverse Events

All of the adverse device effects, serious adverse device effects will be summarized for all subjects who enrolled in this trial in terms the number of events, the percentage of subjects with events and event per AE term. All CEC adjudicated adverse events will also be summarized for all subjects who enrolled in the trial by treatment arms in terms the number of events, the percentage of subjects with events.

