#### Secondary Endpoints:

1. Severe aortic regurgitation (AR) at one year
2. Kansas City Cardiomyopathy Questionnaire (KCCQ) at one year
3. Moderate or severe aortic regurgitation at one year
4. Six-minute walk at one year

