## 9 Adverse Events (Pivotal IDE and CAP)

### 9.1 Unanticipated Adverse Device Effect

Any serious adverse effect on health or safety or any life-threatening problem or death caused by, or associated with a device, if that effect, problem, or death was not previously identified in nature, severity, or degree of incidence in the investigational plan or application, including a supplementary plan or application, or any other unanticipated serious problem associated with the device that relates to the rights, safety, or welfare of subjects (21 CFR 812.3 (s)).

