## 9.5 Classification of Causal Relationships

For each adverse event, the causal relationship between the adverse event and the Portico Transcatheter Heart Valve and Delivery System, and the causal relationship between the event and the index procedure, will be assessed by the Investigator and reported as such on the Adverse Event case report form. Final causal relationships for events related to primary and secondary endpoint criteria according to the Valve Academic Research Consortium (VARC 2) definitions will be determined per CEC adjudication.

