## 10 Independent Boards (Pivotal IDE and CAP)

### 10.1 Clinical Events Committee

An independent Clinical Events Committee (CEC), consisting of, at a minimum, an interventional cardiologist, cardiologist, cardiothoracic surgeon, and a neurologist will adjudicate events related to primary and secondary endpoint criteria according to the Valve Academic Research Consortium (VARC 2) definitions. The CEC will have final adjudication responsibilities for subject outcomes related to primary and secondary endpoint criteria. Members of the CEC cannot be investigators on the PORTICO Clinical

Study. A charter that is agreed upon by both the Sponsor and the independent CEC governs the event adjudication process.

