## 16 APPENDICES

### Appendix A: Abbreviations

Abbreviation	Term
6MWT	Six Minute Walk Test
AA	Alternative Access
ACC	American College of Cardiology
ACT	Activated Clotting Time
ADE	Adverse Device Effect
AE	Adverse Event
AF	Atrial Fibrillation
AHA	American Heart Association
ARB	Angiotensin Receptor Blocker
AS	Aortic Stenosis
AV	Aortic Valve
AVA	Aortic Valve Area
AVR	Aortic Valve Replacement
BARC	Bleeding Academic Research Consortium
BNP	B-type Natriuretic Peptide
CAD	Coronary Artery Disease
CAP	Continued Access Protocol
CAV	FDA Approved and Commercially Available Transcatheter Valve
CBC	Complete Blood Count
CCS	Canadian Cardiovascular Society
CE	Conformité Européene (European Conformity)
CEC	Clinical Events Committee
CIP	Clinical Investigation Plan
CMS	Centers for Medicare & Medicaid Services
CPB	Cardiopulmonary Bypass
eCRF	Electronic Case Report Form
CT	Computed Tomography
CV	Curriculum Vitae
CVA	Cerebral Vascular Accident
DSMB	Data Safety Monitoring Board
ECG	Electrocardiogram
Echo	Echocardiography
eDC	Electronic Data Capture
EEA	European Economic Area
EF	Ejection Fraction

Abbreviation	Term
EOA	Effective Orifice Area
EU	European Union
FDA	Food and Drug Administration
GI	Gastro Intestinal
HOCM	Hypertrophic cardiomyopathy with or without obstruction
ICF	Informed Consent Form
IDE	Investigational Device Exemption
IFU	Instructions For Use
INR	International Normalized Ratio
IRB	Institutional Review Board
ITT	Intent To Treat
KCCQ	Kansas City Cardiomyopathy Questionnaire
Kg	Kilogram
LBBS	Left Bundle Branch Block
LV	Left Ventricular
LVEF	Left Ventricular Ejection Fraction
MAC	Mitral Annular Calcification
MI	Myocardial Infarction
MMSE	Mini-mental state examination
MR	Mitral Regurgitation
MRI	Magnetic Resonance Imaging
mRS	Modified Rankin Scale
MSCT	Multi-Slice Computed Tomography
NCD	National Coverage Determination
NIHSS	NIH Stroke Scale
NYHA	New York Heart Association
PA	Pulmonary Artery
PCI	Percutaneous Coronary Intervention
PCWP	Pulmonary Capillary Wedge Pressure
PI	Principal Investigator
QoL	Quality of Life
PAVR	Percutaneous Aortic Valve Replacement
PMA	Premarket Approval
PVD	Peripheral Vascular Disease
PVL	Paravalvular Leak
RA	Right Atrium
RV	Right Ventricular
SADE	Serious Adverse Device Effect
SAE	Serious Adverse Event

Abbreviation	Term
SAV	Surgical Aortic Valve
SAVR	Surgical Aortic Valve Replacement
SD	Standard Deviation
SJM	St. Jude Medical, Cardiovascular Division
SSC	Subject Selection Committee
STS	Society of Thoracic Surgeons
TA	Trans Apical

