1.6 Blinding

Subjects were not blinded to their assigned treatment. Packaging and design of the Portico and CAVs are different, and thus, implanters were not blinded to the assigned treatment. There was no randomization or blinding of treatment in the FlexNav cohort.

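### Device relatedness is asked for Portico but not for the control valve, and SAP 3.2 states no arm split for device effects, so that summary gives no fair Portico-versus-control comparison.

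*SAP*

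**What the plan says.** Protocol 9.5 asks the investigator for two causality ratings on every adverse event. One is "the causal relationship between the adverse event and the Portico Transcatheter Heart Valve and Delivery System"; the other is the relationship to the index procedure. The control valve is not mentioned.

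The term "Adverse Device Effect" appears in Appendix A as an abbreviation, and no visible section defines it. The one visible definition of a device effect, for unanticipated effects in Protocol 9.1, is worded for any device: "caused by, or associated with a device".

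SAP 3.2 has two sentences. The first reads "All of the adverse device effects, serious adverse device effects will be summarized for all subjects who enrolled in this trial" and does not mention arms. The second reads "All CEC adjudicated adverse events will also be summarized for all subjects who enrolled in the trial by treatment arms". No redaction is visible within Protocol 9.5 or SAP 3.2.

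On adjudication in the pivotal trial, Protocol 10.1 states: "The CEC will have final adjudication responsibilities for subject outcomes related to primary and secondary endpoint criteria". On masking, SAP 1.6 states that "implanters were not blinded to the assigned treatment".

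**The concern.** Protocol 4.1 introduces its risk list as applying to both the study valve and the commercially available control valves. The list includes valve thrombosis, migration, embolization, structural deterioration and stenosis. In a randomized comparison with approved valves, a reader of the report will want to know whether such events were more or less frequent with Portico.

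A table headed adverse device effects looks like the place to find out. If only Portico events can readily earn that label, the table cannot answer the question, and it may mislead in either direction. Pooled, it understates the Portico rate. Split by arm, it makes Portico look worse than control for a reason unrelated to the valves. The people supplying the ratings know which valve was implanted.

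**Working it through.** The documents give no device-effect rate, so there is no plan figure to reproduce. The finding comes from tracing the text; the arithmetic only shows what would follow from it.

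**Tracing a control-valve event, for example a migration some months after implant**

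1. *Reported?* Yes. Protocol 9.4.1 requires all adverse events, in either arm.
2. *Rated for device relatedness?* Protocol 9.5 asks only about Portico, so there is no stated rating that would make it a device effect of the control valve. It is rated against the index procedure.
3. *In the by-arm CEC summary?* Only if it is related to a primary or secondary endpoint criterion. These are death, disabling stroke, life-threatening bleeding with transfusion, kidney injury with dialysis, major vascular complications, aortic regurgitation (for example "Moderate or severe aortic regurgitation at one year"), KCCQ and walk distance. Thrombosis, migration and structural deterioration are not named among them.
4. *In a descriptive endpoint?* In part. Acute device success covers positioning and gradient or velocity at implant, and reintervention for aortic insufficiency is listed. None of the 15 descriptive endpoints names thrombosis, later migration or structural deterioration.
5. *In a by-arm table of all adverse events?* SAP 3.2 does not plan one.

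**Two readings of the device-effect summary**

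Inputs: 750 randomized 1:1 (SAP 1.3 and 1.5), so 750/2 = 375 per arm. Assumed, because not in the documents: true rates r_P (Portico) and r_C (control) of a few percent, and f, the share of control-valve device events that still get classed as device effects, anywhere from 0 to 1.

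*Pooled over the randomized cohort:* printed rate = (375·r_P + 375·f·r_C)/750 = (r_P + f·r_C)/2. With r_P = 3%:

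| r_C | f = 0 | f = 0.5 | f = 1 |
|---|---|---|---|
| 1% | 1.50% | 1.75% | 2.00% |
| 3% | 1.50% | 2.25% | 3.00% |
| 6% | 1.50% | 3.00% | 4.50% |

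At f = 0 the printed figure is half the Portico rate whatever the control valve does. The arms cannot be separated at any f.

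If the phrase about all enrolled subjects also brings in the single-arm Portico groups at their stated maxima (100 FlexNav, 100 FlexNav roll-ins, 100 valve-in-valve), then with equal true rates the f = 0 factor becomes (375 + 300)/(750 + 300) = 675/1050 = 0.64 instead of 0.50.

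*By arm, with 9.5 unchanged and equal true rates r:* apparent Portico excess = r − f·r = r(1 − f). At r = 3% this is 3.0 points at f = 0 (about 11 v 0 subjects, since 375 × 0.03 = 11.25), 1.5 points at f = 0.5 (about 11 v 6) and 0 at f = 1.

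**What an even-handed table would deliver**

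With events counted alike in both arms, the 95% half-width for the difference is about 1.96·√(2p(1−p)/375): 1.4 points at p = 1%, 2.4 at 3% and 3.1 at 5%. That is informative enough to report, though not a powered test.

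**The case against.** The best reply is that little is actually lost. All adverse events are reported in both arms and rated for procedure relatedness, and SAP 3.2 does not itself restrict device effects to Portico. A control event rated procedure-related might be counted.

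Other routes do not depend on 9.5:

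- The CEC covers events related to endpoint criteria, so a valve event leading to death, disabling stroke or significant regurgitation reaches the by-arm summary.
- The leaflet-motion sub-study required CT or TEE at 30 days and 6 months, with no stated limit by arm, until its sample was complete (Protocol 5.1).
- Protocol 7.11 calls for leaflet-motion assessment after ischemic stroke or myocardial infarction.
- Echocardiograms are read by a core laboratory (7.16).
- Appendix C defines an individual patient success that refers to device-related events and valve-related rehospitalization without naming a valve.

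Finally, the adverse event form is not in the documents, and SAP 2.8 to 2.10 and Protocol Appendix S cannot be read.

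Most of this stands, and it sets the limits of the point. A reader might infer that control-valve events go unrecorded, or that the trial's safety comparison as a whole is skewed. The documents do not support either inference. The events are collected, several routes pick up part of them, and the formal safety comparison is the 30-day composite tested in both arms.

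The reply does not rescue the device-effect summary itself. None of those routes gives a control-valve thrombosis or migration a device rating, and nothing in SAP 3.2 tabulates such events by arm without one.

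The reply also bears on the remedy. The SAP already describes blinding in the past tense and the imaging sub-study is complete, so asking sites to re-rate old control events would mean late attribution by people who know the arm.

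**Conclusion.** The point holds for one descriptive table. Read as written, Protocol 9.5 and SAP 3.2 together produce a device-effect summary that cannot fairly compare Portico with control, whether it is pooled or split by arm. SAP 2.2.2, which says categorical results are compared, makes the by-arm reading plausible, but the defect remains under that reading.

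The size is unknown. It depends on event rates and on f, neither of which is in the documents; at f = 1 the by-arm distortion vanishes. The 1.5% and 3-point figures above are illustrations under assumed rates, not estimates. The point is stronger for thrombosis, migration and structural deterioration than for stenosis: early gradients are covered in both arms, and a gradient still better than baseline need not be an adverse event under Protocol 9.2.

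No primary or secondary test, success rule or sample size depends on it. The conclusion rests on the visible text; an adverse event form that already asked about both valves would largely answer it.

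**What to change.** **Main change, in SAP 3.2, for the randomized cohort.** Tabulate adverse events and serious adverse events by term and treatment arm, with that arm's subjects as denominator and regardless of relatedness. Include the valve events listed in Protocol 4.1 and 9.3 (thrombosis, migration or embolization, structural deterioration, stenosis), and give a 95% confidence interval for the between-arm difference in each of these.

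**Device effects.** Present Portico-related effects for Portico-treated subjects only, with that denominator. Do not set them against control unless relatedness was collected for both valves. Adding an arm split to the present first sentence and changing nothing else would display the artefact, not remove it.

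**Events still to be reported.** Protocol 9.5 and the adverse event form can ask about the implanted transcatheter valve, Portico or control, and its delivery system.

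**Cost.** The main table uses data already collected in both arms and needs no re-rating of past events. Its drawback is that it includes some events unrelated to the valve. The wording change in 9.5 is small if applied forward only; applied backward it would require unblinded re-attribution, which I would avoid.
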